This project is theoretically innovative because it conceptualizes prenatal depressive symptoms and cannabis use as key factors for tobacco use during pregnancy and in the postpartum. Moreover, it frames that research question in the context of intersecting identities and experiences that may promote tobacco use before, during, and after pregnancy and hamper cessation efforts, contributing to lapse and relapse. It is methodologically innovative to elevate the voices of those with lived experiences of depressive symptoms, tobacco, and cannabis use to co-develop an intervention for prenatal tobacco cessation with real world impact. Human centered design (HCD) and IM are powerful methods to translate community perspectives into workable solutions for pregnant people who smoke. Demonstrating the importance of addressing depressive symptoms and cannabis use for success in prenatal smoking cessation also has significant implications for clinical practice. Collaboratively developing an intervention will enable us to design an intervention that incorporates minoritized people’s views and lived experiences of depression, stress, discrimination, stigma, trauma and other contexts in a way that is distinct from previous “one-size fits most” approaches in other prenatal substance use interventions. Members from minoritized groups will adapt intervention parameters that address their needs, contexts that should be emphasized, and which elements are less relevant to their circumstances.

D2. Preliminary results

The investigative team has conducted prior research examining health disparities in

prenatal substance use as well as relations among prenatal depressive symptoms, cannabis use and tobacco use. Most participants in the YoungMoms project are Black or Biracial (78%) and one-third identify as something other than strictly heterosexual (21% are bisexual). As seen in Figure 2, sexual minority (SM) participants in the YoungMoms study are more likely to smoke during pregnancy compared to those who identified as heterosexual ([name] et al., under review). In qualitative interviews, some SM participants linked their experiences as a SM and related mental health with prenatal tobacco use. The results of this and other research (e.g., Beck et al., 2021; Gonzalez et al., 2019; King et al., 2020) demonstrate that pregnant SM people need to be included in research related to prenatal tobacco and cannabis use.

Our research has also shown that there are long-term associations between cannabis and tobacco use before, during, and after pregnancy. For example, cannabis was associated with combustible cigarette use in adolescent parents and those who used cannabis were significantly less likely to quit smoking cigarettes 10 years postpartum ([name] et al., 2009). In another study, a history of any cannabis use was associated with cigarette use during pregnancy and 6 months postpartum, suggesting that assessing history of cannabis use early in pregnancy might be useful in determining risk for prenatal and postpartum tobacco use ([name], Germeroth, et al., 2021). In trajectory analyses, we have shown that prenatal cannabis use was related to cigarette use spanning the prenatal period to 16 years postpartum ([name] et al., 2017). Thus, it is crucial to address prenatal cannabis use in interventions promoting tobacco cessation and prevention of relapse to smoking in the postpartum.

Using a latent class analysis of YoungMoms data, we found that the class with highest probability of clinically significant depressive symptoms also had the highest probabilities of prenatal tobacco and cannabis use, as verified by urine screening (Hill et al., 2022). This class was more likely to be non-Hispanic Black, Biracial, or Hispanic and reported more prenatal stress, morning sickness, and unintended pregnancy (Hill et al., 2022). We have found self-reported and/or positive screen for prenatal tobacco and cannabis use, and emotional distress scores to be significantly related to prenatal dual use, even after controlling for household nicotine and cannabis use and sexual minority status. These results underscore the role of depressive symptoms in prenatal dual use of tobacco and cannabis ([name], Richardson et al., 2021).

Relatedly, we examined the effectiveness of two postpartum smoking relapse preventions as a function of prenatal depressive symptoms ([name] et al., 2020). People with clinically significant depressive symptoms late in pregnancy did not maintain smoking abstinence in the postpartum if they received a standard intervention with behavioral techniques to manage cigarette cravings (SUPPORT). However, as seen in Figure 3, those who were depressed late in pregnancy were more successful maintaining abstinence if they received a smoking abstinence intervention that was tailored to psychosocial factors such as mood (STARTS). These results highlight the importance of depressive symptomatology in postpartum tobacco abstinence and the significance of addressing prenatal depressive symptoms for long-term impact on maternal and child health. Thus, we propose to

invite people who use tobacco and cannabis and experienced elevated depressive symptoms during pregnancy to partner with us in an intervention development project to reduce tobacco-related health inequities.

Study Design

1. Total number of subjects to be enrolled at this site (enter -1 for chart reviews, banking, registries):

25

2. Describe and explain the study design:

This study is an experimental, single-arm feasibility trial.

3. Describe the primary and secondary study endpoints:

The primary outcomes of the trial is the feasibility and acceptability of the novel intervention and abstinence from tobacco and cannabis use. Feasibility and acceptability of the intervention will be assessed using attendance, completion of intervention-related procedures, and the Acceptability of Intervention Measure (AIM). Abstinence will be measured by proportion of the participants who self-report no use of either substance and by calculating the proportion of participants with negative urine screens for THC and COT. Secondary outcomes include changes in depressive symptoms, tobacco, and cannabis use from the baseline assessment in pregnancy to 3 months postpartum.

4. Provide a description of the following study timelines:

Duration of an individual subject's active participation:

Depending on gestation age at enrollment, subjects will actively participate in the study for approximately 6 to 12 months.

Duration anticipated to enroll all subjects:

9/30/2026

Estimated date for the investigator to complete this study (complete primary analyses):

10/1/2027

5. List the inclusion criteria:

- (1) <26 weeks of gestation
- (2) English speaking
- (3) confirmed pregnant
- (4) plan to remain pregnant
- (5) use of combustible tobacco at least once a week during pregnancy, or at least once a week in the 3 months before pregnancy if stopped
- (6) use of cannabis at any frequency during pregnancy or in the 3 months before pregnancy if stopped

English speaking is a requirement since study materials are in English and intervention sessions will be conducted in English.

6. List the exclusion criteria:

- (1) current opioid use or active treatment for Opioid Use Disorder
- (2) unable to provide informed consent in English
- (3) under 18 years old

7. Will children or any gender, racial or ethnic subgroups be explicitly excluded from participation?

☒ Yes ☐ No

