In addition to the incentive for completing assessments, we have budgeted up to \$50 for a clean (i.e., no evidence of tobacco and cannabis use) sample as a contingency management incentive at the final postpartum assessment (T4).

Participants will be paid using Vincent, the University's approved payment system. There will be no compensation for partial completion of T1, T2, or T3. At T4, participants will be paid separately for completing all questionnaires (\$75) and interviews (\$25).

5. Recruitment materials: (attach all material to be seen or heard by subjects, including advertisements and scripts)

	Document	Category	Date Modified	Document History
View	Recruitment Scripts(1)	Recruitment Materials	2/3/2026	History
View	Intervention Screening Survey(2)	Recruitment Materials	1/30/2026	History
View	Recruitment flyer(1)	Recruitment Materials	1/6/2026	History

Study Aims

1. * Describe the purpose, specific aims, or objectives and state the hypotheses to be tested:

Guided by the PICTURe community collaborative, we will conduct a single group, proof-of-concept feasibility trial of a new intervention designed to address prenatal depressive symptoms to encourage tobacco and cannabis cessation. We will examine the initial feasibility and acceptability of the intervention using standard measures in addition to measures suggested by the collaborative. We hypothesize that 1) the intervention will be feasible to participants and 2) the intervention will be acceptable to participants.

The primary outcomes of the trial are the feasibility and acceptability of the novel intervention and abstinence from tobacco and cannabis use. Feasibility and acceptability of the intervention will be assessed using attendance, completion of intervention-related procedures, and the Acceptability of Intervention Measure (AIM). Abstinence will be measured by proportion of the participants who self-report no use of either substance and by calculating the proportion of participants with negative urine screens for THC and COT. Secondary outcomes include changes in depressive symptoms, tobacco, and cannabis use from the baseline assessment in pregnancy to 3 months postpartum.

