*** Identify the subgroups and provide a justification:**

We exclude individuals under age 18 from this work because the perinatal concerns and treatments for depression of individuals younger than age 18 are likely to differ from those of individuals 18 years of age or older and would require developmentally appropriate assessments and interventions.

8. Describe the power analysis used and cite your method of statistical analysis. If a power analysis is not possible, thoroughly justify the sample size required for the study, including appropriate literature citation (alternatively provide page reference in attached protocol):

Chi-square tests will be used to calculate differences in feasibility as a function of key intersecting identities (e.g., age, race, ethnicity, SM status) and use history variables. If feasibility is found to be significantly different by race or SM status, the analyses will be weighted to account for differences in attrition. We will assess the preliminary efficacy of the novel intervention to promote self-reported abstinence from tobacco and cannabis at the end of pregnancy (Time 3) and 12-16 weeks postpartum (Time 4). The proportion of self-reported abstinence among participants in the INT and EUC groups at Times 3 and 4 will be compared using chi-square tests of difference. We will stratify by race and sexual orientation to test for intersectional effects. Secondary analysis will examine differences in biochemically verified abstinence (urine dip test for presence of cotinine or THC) and depressive symptoms between INT and EUC using chi square tests and compare depressive symptoms (EPDS) scores in the two groups using two-sample t-tests. The Cochran Q test will be applied to self-reported tobacco and cannabis use across the 4 time points within the INT group to test whether there has been a change in the ratings over time. Next, a generalized linear mixed effects model (GLMM) with a logit link will be used to test the treatment effect (INT vs. EUC) and treatment by time interaction to test whether the rate of abstinence over time was steeper among the INT group compared to the EUC group. We have 70% power to detect a 15% difference in quit rates between INT and EUC, assuming a 25% intervention arm quit rate and 10% control arm quit rate.

Pregnant Women

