5: Mindfulness skills. This may include teaching of nonjudgmental emotional awareness, nonjudgmental awareness of management of urges, and trauma-informed adaptations to mindfulness practice.

End of Intervention Assessment (T2):

This assessment will occur when participants are 32-36 weeks gestation. Participants will complete the following questionnaires on REDCap as part of the end-of-intervention assessment: Demographics, EPDS, Smoking and Alcohol Use Questionnaire, Cannabis Use Questionnaire, Perceived Stress Scale-4, and Everyday Discrimination Scale. Participants will be paid \$50 using the Pitt Vincent payment system when questionnaires are completed.

1-month Postpartum Assessment (T3):

Participants will complete the following questionnaires on REDCap as part of the 1-month postpartum assessment: Demographics, EPDS, Smoking and Alcohol Use Questionnaire, Cannabis Use Questionnaire, Perceived Stress Scale -4, and Everyday Discrimination Scale. Participants will be paid \$70 using the Pitt Vincent payment system when questionnaires are completed.

3-month Postpartum Assessment (T4):

This assessment will be scheduled to occur in person at Bellefield Towers or at an agreed upon location convenient to the participant. Participants will complete the following questionnaires and interviews: Demographics, EPDS, Smoking and Alcohol Use Questionnaire, Cannabis Use Questionnaire, Perceived Stress Scale-4, Everyday Discrimination Scale, Acceptability of Intervention (AIM), Additional Treatments, Timeline Follow-back and OB/Neonatal outcomes. Following completion of the questionnaires and interviews, participants will be paid \$100 using the Pitt Vincent payment system. Participants will be asked to provide a urine sample as contingency management, which will be tested for the presence of cotinine (COT) and THC. Participants will receive an additional \$50 if their sample tests negative for both substances.

Urine collection:

Participant will be provided with a sterile urine collection cup and directed to a nearby bathroom where they can collect their sample independently. Participants will be offered an opaque bag to transport urine sample cup back to the assessment location. Research staff will follow testing procedures for the THC and COT dip tests and then dispose of all testing and collection equipment in a hazardous waste bin or bag.

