De-identified data from the project will be saved in a database prepared for the study. The database will be password protected. The MPIs will make deidentified data collected from research participants available to other researchers and community partners after the study is completed and the final report has been generated. Data will be provided in the form of Excel files containing only ID codes as subject identifiers. No identifying information, including names, telephone numbers, or addresses, will be made available. Researchers requesting use of data must submit their request in writing to the MPIs, including the purpose for which they are requesting use of the data. These requests will be reviewed by the Investigators and will require engaging in a Data Use Agreement (DUA), in cooperation with the University of Pittsburgh. Data will be of sufficient quality to allow other investigators to validate and replicate research findings, consistent with NOT-OD-21-013. Updates on data sharing activities will be provided in annual progress reports to the funding organization.

- 3. If any research data is collected, stored, or shared in a paper format, address what precautions will be used to maintain the confidentiality of the data:**

Paper documents are kept in locked filing cabinets in an office of the Western Psychiatric Hospital at the University of Pittsburgh. Access to subject data records will be given only to the PI and study staff supervised by Drs [name] and [name].

Specimens and Related Data

1. * Data and Specimens will be stored:

Limited time (i.e., only until the study is completed)

2. * Indicate the type of specimen, describe where stored, and for how long:

Participants will be asked to provide one urine sample during their final assessment.

The sample will be tested for cotinine and THC and then disposed of immediately after this testing.

3. * How the specimens will be accessed and who will have access to the specimens:

The urine sample will be collected by the participant and accessed only by the research staff testing the sample.

4. * List the data to be stored or associated with each specimen:

The results of the THC and cotinine dip tests, date and time of the test, participant ID number, and documentation of payment for negative results will be recorded in a secure study database.

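### Abstinence is worded as one joint tobacco-and-cannabis result, and its verified form rests on a single T4 urine dip with no self-report check and no look-back period

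*Protocol*

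**What the plan says.** Study Aims item 1, repeated in Study Design item 3, lists abstinence among the primary outcomes and gives two measures. The first is self-report: "Abstinence will be measured by proportion of the participants who self-report no use of either substance". The second is urine: "by calculating the proportion of participants with negative urine screens for THC and COT". Each is written as one proportion spanning both substances, and neither carries a look-back period.

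Study Design item 8 uses self-reported abstinence at Times 3 and 4 for preliminary efficacy. It then adds: "Secondary analysis will examine differences in biochemically verified abstinence (urine dip test for presence of cotinine or THC". Self-report is not part of that description.

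On sampling, Specimens and Related Data item 2 states: "Participants will be asked to provide one urine sample during their final assessment". In the T4 paragraph of Research Activities item 1, the extra payment is made "if their sample tests negative for both substances". Specimens and Related Data item 4 shows that the stored data include "The results of the THC and cotinine dip tests, date and time of the test, participant ID number". The T4 visit also includes the smoking and cannabis questionnaires and "Additional Treatments, Timeline Follow-back and OB/Neonatal outcomes".

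No section gives a cut-off, detection window or clearance time for either dip.

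**The concern.** Two things are being asked of one dip result.

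First, it stands for abstinence from two substances at once. The trial targets both, and section B7 of the background argues that treating mood may help sustain tobacco abstinence after delivery. A joint result cannot show tobacco cessation in someone who is still THC-positive.

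Second, it is called verified abstinence although nothing requires it to agree with what the participant reports at the same visit. A dip reflects only a limited period before the sample. Without a stated look-back, neither a negative nor a positive result says over what period the participant was or was not abstinent. Section B1 says most return to smoking happens within 100 days of delivery, and T4 falls at 12–16 weeks (84–112 days). The visit is well timed, but one undated dip cannot describe that interval.

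At stake is what the trial can say about each substance, and whether its verified figure bears that name.

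**Working it through.** The plan gives no expected urine-negative proportion and no misclassification rate, so there is no figure of its own to reproduce. The check has three parts.

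**1. Apply the wording to individual cases at T4.** COT is the cotinine dip.

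| Participant | COT dip | THC dip | Joint urine result | Joint self-report result |
|---|---|---|---|---|
| A: reports no use of either | − | − | abstinent | abstinent |
| B: reports tobacco use some days before T4 | − | − | abstinent | not abstinent |
| C: quit tobacco, still uses cannabis | − | + | not abstinent | not abstinent |
| D: quit tobacco, stopped cannabis shortly before T4 | − | + | not abstinent | depends on the look-back, which is not stated |
| E: quit neither | + | + | not abstinent | not abstinent |

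B is verified abstinent on the dip while her own report says otherwise. C, D and E share one urine result although C and D have stopped tobacco. These two findings follow from the wording and need no pharmacology beyond the possibility of each dip pattern.

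**2. How far back might a dip reach?** All inputs here are assumptions, because the documents give none. Time to negative = half-life × log2(starting concentration / cut-off).

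- Cotinine, short end: 16 h × log2(1000/200) = 37.2 h = 1.55 days.
- Cotinine, long end: 20 h × log2(2000/50) = 106.4 h = 4.43 days.
- THC metabolite, short end: 2 d × log2(100/50) = 2.0 days.
- THC metabolite, long end: 6 d × log2(500/20) = 27.9 days.

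Against 84–112 days from delivery to T4, cotinine covers 1.55/112 = 1.4% to 4.43/84 = 5.3%. THC covers 2.0/112 = 1.8% to 27.9/84 = 33%. The ranges overlap at the low end, so the windows differ materially only if cannabis use is heavy or clearance is slow.

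**3. Effect on the both-negative proportion.** Let p be true abstinence over whatever look-back is intended, f1 the share of true abstainers still THC-positive, and f2 the share of users negative on both dips. Then observed proportion = p(1 − f1) + (1 − p)f2. The values p = 25% and 10% are the two quit rates in Study Design item 8. The ranges f1 = 0 to 0.4 and f2 = 0 to 0.2 are assumptions.

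- p = 0.25, f1 = 0.4, f2 = 0: 0.25 × 0.6 = 15%.
- p = 0.25, f1 = 0, f2 = 0.2: 0.25 + 0.75 × 0.2 = 40%.
- p = 0.25, f1 = 0.4, f2 = 0.1: 0.15 + 0.075 = 22.5%, close to the truth because the errors nearly cancel.
- p = 0.10: from 0.10 × 0.6 = 6% to 0.10 + 0.90 × 0.2 = 28%.

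For scale, one participant in 25 is 1/25 = 4 points, and the exact 95% interval for 6/25 is 9% to 45%.

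**The case against.** The best case against this has four parts.

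*The urine outcome may not be a composite.* Joint scoring is explicit only for the payment. The outcome phrase could be read as two proportions, and both dip results are stored. Part of this stands: the data allow separate reporting. But no section defines a urine outcome per substance, and the self-report measure beside it is plainly joint.

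*Self-report already covers older use.* It is a parallel measure, and item 8 makes it the efficacy measure, with the dip secondary. That limits the damage: participant B is caught by the self-report proportion. But that measure is also joint and undated, and nothing combines it with the dip, so B still enters the verified figure.

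*A both-negative criterion suits a trial of cessation of both substances.* It does, as one summary. It cannot serve as the only urine summary if the trial is to say anything about tobacco or cannabis separately.

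*An analysis plan may settle look-backs and tables.* It may, and their absence alone would not be a finding. The point is that the protocol itself sets the outcome and describes the verified version without self-report.

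Three stronger readings are tempting and are not supported. A reader might infer that the dip misses recent smoking. A short-window marker does the reverse: it detects the latest use and misses use older than its window. A reader might infer that cannabis quitters in general are scored as users. Only those who stopped shortly before T4 could be, and whether that is an error depends on the look-back intended. A reader might infer a bias of known direction. The documents give no cut-offs or clearance times, and the two errors oppose each other.

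**Conclusion.** The point holds as a defect of outcome definition. From the wording alone, the urine result merges two substances, and verified abstinence can include someone who reports use at the same visit. It also cannot separate a participant who quit tobacco but is THC-positive from one who quit neither.

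The size is not established. The 15% to 40% range around a true 25% rests entirely on assumed error rates, and the net bias cannot be signed. In a 25-person feasibility trial whose stated hypotheses concern feasibility and acceptability, sampling error is of similar width. The consequence is therefore about interpretation: what may be concluded for tobacco, for cannabis, and under the label verified. It is worth correcting because the correction uses data already planned.

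**What to change.** In Study Aims item 1 and Study Design items 3 and 8:

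- Report the cotinine-negative and THC-negative proportions separately at T4, with the both-negative proportion as an additional descriptive result. Label all three as T4 point-prevalence.
- Define verified abstinence for each substance as a negative dip plus no self-reported use, from the T4 questionnaire or Timeline Follow-back, over a look-back that the sponsor pre-specifies for that substance. State which self-report source governs. The documents give no basis for a particular length, so none is proposed here.
- Tabulate the discordant cases: THC-positive with no reported use in the look-back, and dip-negative with reported use, by substance.

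No new visit, sample or instrument is needed. The cost is revised outcome wording and one small table. There will be two headline proportions instead of one. Verified abstinence for a substance may come out slightly lower than its dip-negative proportion, because adding a self-report condition can only remove participants.

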The intervention will be considered feasible and acceptable if participants attend more than 70% (i.e., >4) of sessions. Differences in feasibility also will be compared according to demographic variables and use history variables. Acceptability will be assessed by completion of self-monitoring forms, attendance during pregnancy, and the Acceptability of Intervention (AIM) measure. Retention also will be documented and will be defined as the proportion who provide data at 12-16 weeks postpartum relative to the total number enrolled. We will present these measures of feasibility and acceptability to the collaborative to solicit their input and may add other measures of feasibility and acceptability based on their recommendations.

2. * Describe the relevant prior experience and gaps in current knowledge including preliminary data. Provide for the scientific or scholarly background for, rationale for, and significance of the research based on existing literature and how it will add to existing knowledge:

B. SIGNIFICANCE

B1. People from marginalized communities are more likely to use tobacco during pregnancy (Agrawal et al., 2019) and are under-represented in tobacco treatment research (Weinberger et al., 2022). Rates of prenatal tobacco use have not decreased among Black people (Agrawal et al., 2019; Li et al., 2018) and are higher for sexual minority people (Beck et al., 2021; Gonzalez et al., 2019). At least 40% of individuals who quit smoking during pregnancy will resume smoking in the postpartum (Fingerhut et al., 1990; Rockhill et al., 2016), most of them within 100 days of delivery ([name] et al., 2022). Younger, less educated, Black people are more likely to relapse to smoking postpartum (Orton et al., 2018; Rockhill et al., 2016) and, on average, Black people smoke for more years prior to quitting (Jones

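### Abstinence is named a primary outcome, but the hypotheses and success rule omit it, and its planned between-group tests need a control group that this single-arm trial lacks

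*Protocol*

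**What the plan says.** **Status in the endpoint text.** Study Design, item 3, states: "The primary outcomes of the trial is the feasibility and acceptability of the novel intervention and abstinence from tobacco and cannabis use". Study Aims, item 1, says the same. Both define abstinence in two ways. The first is self-report: "Abstinence will be measured by proportion of the participants who self-report no use of either substance". The second counts those whose urine tests negative for cotinine and THC. Neither gives a threshold or a time point.

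**Hypotheses and success rule.** Study Aims, item 1, states two hypotheses: "We hypothesize that 1) the intervention will be feasible to participants and 2) the intervention will be acceptable to participants". The only success rule follows: "The intervention will be considered feasible and acceptable if participants attend more than 70% (i.e., >4) of sessions". Neither mentions abstinence.

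**Status in the analysis text.** Study Design, item 8, says of the self-report measure: "We will assess the preliminary efficacy of the novel intervention to promote self-reported abstinence from tobacco and cannabis", read at Times 3 and 4. Of the urine measure it says: "Secondary analysis will examine differences in biochemically verified abstinence". Both are to be compared between INT and EUC by chi-square. A logit mixed model with treatment and treatment-by-time terms follows, then a power sentence (70% power, 25% versus 10%). Cochran's Q is planned within INT.

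**Design.** Study Design, item 2: "This study is an experimental, single-arm feasibility trial". Item 1 gives a total of 25.

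**Who may enter.** Inclusion criteria 5 and 6 admit people who used tobacco and cannabis in the 3 months before pregnancy and have since stopped.

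**The concern.** The primary outcome, the hypotheses, the success rule and the analysis are all fixed in this one document, and on abstinence they disagree. It is primary in two places, is absent from the hypotheses and the rule, and has a lower standing in the analysis section. The tests that would give it a conclusion cannot be run.

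What is at stake is how the result will be reported. A primary label invites an uncontrolled abstinence proportion in 25 people to be presented as a finding about efficacy. With no preset bar, much the same proportion could be called promising or disappointing once it is known. Since some participants may already be abstinent at entry, the figure would partly reflect who enrolled.

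**Working it through.** **1. The passages side by side**

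| Outcome | Endpoint text (Study Aims 1, Study Design 3) | Hypothesis | Success rule | Analysis text (Study Design 8) |
|---|---|---|---|---|
| Feasibility, acceptability | Primary | Yes | Attendance above 70% of sessions | Chi-square for feasibility by identity and use history |
| Self-reported abstinence | Primary | None | None | Preliminary efficacy, INT vs EUC |
| Urine-verified abstinence | Primary | None | None | Secondary, INT vs EUC |

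Every INT versus EUC entry needs a second group, and the design provides one group.

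**2. The plan's own power figure**

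Inputs from item 8: p1 = 0.25, p2 = 0.10, power 0.70, chi-square. Alpha and sidedness are not stated; two-sided 0.05 is assumed, with looser choices shown.

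n per arm = [z(1−α/2)·√(2·p̄·(1−p̄)) + z(power)·√(p1(1−p1) + p2(1−p2))]² / (p1−p2)², with p̄ = 0.175.

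- √(2 × 0.175 × 0.825) = √0.28875 = 0.5374
- √(0.1875 + 0.09) = √0.2775 = 0.5268
- n = (1.960 × 0.5374 + 0.524 × 0.5268)² / 0.0225 = 78.6, so 79 per arm and 158 in total

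| Variant | n per arm for 70% | Power if 25 are split 12.5/12.5 | Power at 25 per arm |
|---|---|---|---|
| Two-sided 0.05 | 79 (92 with continuity correction) | 16% | 28% |
| One-sided 0.05 | 60 | 25% | 40% |
| One-sided 0.10 | 42 | 38% | 55% |

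The stated 70% is not reproduced under any variant. Even the loosest needs 84 people in two arms. The sentence therefore cannot serve as a bar for abstinence here.

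**3. What 25 people in one arm can show**

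Exact (Clopper-Pearson) 95% limits for x of n: lower = Beta quantile 0.025 with parameters (x, n−x+1); upper = Beta quantile 0.975 with parameters (x+1, n−x).

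| Abstinent | Proportion | Exact 95% interval |
|---|---|---|
| 2/25 | 8% | 1.0% to 26.0% |
| 3/25 | 12% | 2.5% to 31.2% |
| 6/25 | 24% | 9.4% to 45.1% |

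These assume that all 25 give data. Losses would widen them.

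**4. Baseline status**

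The protocol does not say how many will have stopped both substances by enrolment. If 6 of 25 are abstinent at T4, anywhere from 0 to 6 of them may already have been abstinent at T1. The same 24% is compatible with six new quitters or with none.

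**5. When each measure exists**

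Research Activities, item 1, collects tobacco and cannabis questionnaires at T1 to T4. Urine is taken once, at T4 (confirmed in Specimens and Related Data, item 2). Verified abstinence is therefore available at T4 only. Item 8 also places Time 3 at the end of pregnancy, whereas Research Activities places T3 at 1 month postpartum, so visits should be named by their timing.

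**The case against.** **The result already has a reading.** A reader might infer that high attendance with few abstinent would leave the trial neither a success nor a failure. The documents do not support that. Feasibility and acceptability have their own rule, the hypotheses concern only those two, and the protocol claims no single overall verdict. Such a result would read as feasible with little sign of abstinence. This objection stands.

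**No hierarchy is required.** A proof-of-concept trial needs no formal alpha hierarchy, and all-or-any rules are commonly left to an analysis plan. This stands too. It does not excuse labels that disagree within one document.

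**Change in use as a secondary outcome.** This might look like a contradiction. It is not: abstinence is a state, and change from baseline is a different quantity.

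**The 10% rate as a benchmark.** One might argue that 6/25 decides nothing because its interval contains 10%. That rate belongs to the EUC comparison, which cannot be made, and the argument depends on the interval chosen: the exact one-sided probability of 6 or more of 25 at 10% is 0.033. The intervals above show precision only.

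**Some analysis can be run.** Cochran's Q within the one group needs no control. It tests change over time and sets no success bar.

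**Abstinence could stay primary.** The intervention is meant to encourage cessation, so this is defensible if a measure, time point, bar and rank are stated. For illustration, with 10% as null and 25% as target in 25 people, a bar of at least 5 gives one-sided alpha 0.098 and power 0.786; at least 6 gives 0.033 and 0.622. Those rates are not clean references when people who have already stopped may enrol.

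**Conclusion.** The point holds as a conflict over the status of abstinence, together with between-group analysis text that does not fit the design. Abstinence is primary in two statements, has no hypothesis or bar, is ranked lower in item 8, and has no between-group test that can be run in one arm. The power sentence would need 158 people at two-sided 0.05, or 84 under the loosest variant tried, against 25 planned.

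The consequence is limited to what may be claimed about abstinence. The feasibility conclusion is untouched, taking the attendance rule as written. The documents do not support the wider inference that the trial as a whole cannot be interpreted. The power results rest on the assumed alpha and sidedness, and the intervals on 25 evaluable participants. That a raw proportion cannot be read as efficacy rests on the absence of a control group and on the eligibility criteria.

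**What to change.** 1. **Study Aims, item 1, and Study Design, item 3.** Keep feasibility and acceptability, judged by the stated attendance rule, as the primary outcome. Report AIM descriptively unless a threshold is set; making it co-primary without one would give another primary outcome with no bar. List abstinence as secondary, beside change in tobacco and cannabis use.
2. **Study Design, item 8.** Remove the INT versus EUC chi-square tests, the two-sample t-tests, the mixed model and the power sentence. Replace them with descriptive estimates: self-reported abstinence as a proportion with exact 95% interval at each assessment, shown beside T1 status; urine-verified abstinence at T4 only; and depressive symptom scores summarised within the single group. If Cochran's Q is kept, label it exploratory. State that no efficacy claim will be made.
3. **Precision.** State what 25 people provide, for example 6/25 = 24%, exact 95% interval 9% to 45%.
4. **Registration.** Make the entry match.

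The change needs no new data, visits or participants, and is best made before any outcome is known. Its cost is an amendment to the primary outcome as well as to wording: abstinence can no longer be headlined as a primary result. Keeping it primary with a stated measure, time point, bar and rank would also remove the conflict, but would still not support an efficacy claim.
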